## 6.10 Pharmacokinetic Analyses

### 6.10.1 Sample Collections for Pharmacokinetic Analyses

Blood samples will be collected to profile the levels of ATR-101 and its metabolites on Day 1 of each Dose Level at pre-dose and 1, 2, 3, and 4 hours post-dose; on Day 15 of each Dose Level at pre-dose, and at the Final Study Visit or Early Termination Visit. A window of  $\pm 10$  minutes is permitted around each sampling time point.

The exact time of each sample collection will be recorded. If the exact time (measured from dosing) is outside of the collection window for nominal time points, the corresponding concentration will be excluded from concentration versus time descriptive statistical summaries and plots, but will still be used in the calculations of PK parameter estimates.

### 6.10.2 Pharmacokinetic Variables

The PK parameters listed below will be calculated from the individual plasma concentration profiles by standard non-compartmental methods:

**Table 2. PK Parameters to be Calculated**

$C_{\max}$	Maximum observed concentration
$t_{\max}$	Time to reach the maximum observed concentration
$AUC_{0-\text{last}}$	Area under the concentration-time curve calculated from time zero to the last measurable concentration
$AUC_{0-4}$	Area under the concentration-time curve calculated from time zero to 4

	hours
Lambda z ( $\lambda_z$ )	Apparent first-order terminal elimination rate constant calculated by linear regression of the terminal linear portion of the log concentration vs. time curve (data permitting)
$t_{1/2}$	Apparent terminal half-life (data permitting)
AUC 0-inf	Area under the concentration-time curve from time zero to infinity (extrapolated) (data permitting)

### 6.10.3 Pharmacokinetic Variables Calculation

[figure not shown]
Actual collection times will be used in PK parameter calculations. The Linear Trapezoidal Linear Interpolation method will be used in the computation of all AUC values. The PK parameters  $\lambda_z$ ,  $t_{1/2}$ , and AUC0-inf will not be presented for those subjects who do not exhibit a terminal elimination phase in their concentration versus time profiles. In order to estimate the apparent first-order terminal elimination constant,  $\lambda_z$ , linear regression of concentration in logarithm scale vs. time will be performed using at least 3 data points. Uniform weighting will be selected to perform the regression analysis to estimate  $\lambda_z$ . The constant  $\lambda_z$  will not be assigned if:

- the terminal elimination phase is not linear (as it appears on a semi-logarithmic scale)
- the terminal elimination rate constant indicates a positive slope ( $\lambda_z > 0$ )
- $t_{max}$  is one of the 3 last data points
- the regression coefficient ( $R^2$ ) is less than 0.8

If the percent extrapolated AUC0-inf is greater than 20%, the PK parameters will be reported but flagged in the appropriate listing. In cases where the  $\lambda_z$  interval is not assigned, the values of associated parameters ( $\lambda_z$ ,  $t_{1/2}$ , AUC0-inf) will not be calculated.

For the calculation of AUC0-4 if the nominal (planned) time of the last observed measurable concentration is at 4 hours but the actual time of the last observed measurable concentration ( $t_{last}$ ) is less than 4 hours (such as actual time = 3.9 hours), the concentration at 4 hours will be imputed. The imputed concentration is calculated using the linear extrapolation of the previous two records. If the extrapolated concentration is less than 0, then a value of 0 will be used. If the nominal time of the last observed measurable concentration is less than 4 hours, then AUC0-4 will not be calculated. A visual aide for the imputation of the concentration at 4 hours is provided below in Figure 3.

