6.9 Pharmacokinetic Assessments

Blood samples will be collected to profile the levels of ATR-101 and its metabolites at multiple days and times throughout the study. Assessment of ATR-101 levels may help to determine or establish pharmacokinetic and pharmacodynamic relationships. ATR-101 exposure levels may also help in the assessment of safety events. Sampling time points are presented for each of the applicable study days in Table 4. Samples for PK analysis will be taken prior to the first dose of ATR-101 (for each dose level) and up to 4 hours, post-dose. This time period is designed to capture the C_{max} (T_{max} is approximately 2 hours) and a few additional time points. Following the completion of the 14 day ATR-101 dosing period a single PK sample will be collected to assess trough levels of ATR-101 (morning of day 15). Subjects will then enter the 14 day placebo Washout Period. After completion of the placebo Washout period, subjects will either proceed to the next Dose Level and perform the same PK sampling as Day 1, or subjects will complete the Final Study Visit and do the same PK sampling as Day 15.

PK results will not be used to determine dose escalation. Approximately 4 mL of blood will be drawn at each sampling time point.

Table 4 Pharmacokinetic Sampling Time Points.

Visit	Sampling Time Point
Dose Level N, Day 1	Pre-dose, post-dose at 1, 2, 3, and 4 hours
Dose Level N, Day 15	Pre-dose, single blood draw

N=Dose Levels 1-5

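### SAP 6.10.3 contradicts itself on the sign of lambda-z, and its Tmax rule limits half-life and AUC0-inf to profiles that peak by the 1 h sample.

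*SAP*

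**What the plan says.** SAP Table 2 describes lambda-z as the "Apparent first-order terminal elimination rate constant calculated by linear regression of the terminal linear portion" of the log-concentration curve. It lists lambda-z, half-life and AUC0-inf conditionally, where the data permit.

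SAP 6.10.3 requires at least three points for the regression. It withholds lambda-z, and with it half-life and AUC0-inf, in four cases. Two matter here:

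- "the terminal elimination rate constant indicates a positive slope", followed in brackets by lambda-z > 0;
- tmax "is one of the 3 last data points".

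The other two are a terminal phase that is not log-linear and an R-squared below 0.8. If more than 20% of AUC0-inf is extrapolated, the values are still reported but flagged in a listing.

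SAP 6.10.1 sets the Day 1 samples for each "Dose Level at pre-dose and 1, 2, 3, and 4 hours post-dose", with a window of 10 minutes either side. Protocol 6.9 says that Tmax "is approximately 2 hours". For Day 15, it says that "a single PK sample will be collected to assess trough levels of ATR-101".

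SAP 6.10.4 summarises the Day 1 PK parameters by dose level and adds geometric means and geometric CVs for Cmax and all AUCs.

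**The concern.** There are two separate problems.

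The first is the sign. The words of the bullet exclude a rising terminal phase. The bracketed symbol, read with Table 2, excludes every declining one. A programmer who codes the symbol gets the reverse of what the words ask for.

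The second is the combination of the Tmax rule with a 4-hour profile. Barring tmax from the last three points is a reasonable safeguard in itself. With only four post-dose samples, however, it admits only early peaks, and the protocol expects a later one. Half-life and AUC0-inf would then be summarised by dose level from whichever profiles happened to peak early. That set may differ from one dose level to the next, so an apparent dose trend in these parameters could reflect who qualified rather than how the drug behaves. The extrapolation flag does not prevent this, because it acts only in a listing and nothing removes flagged values from the summaries.

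**Working it through.** The plan states no figure for this point, so there is none to reproduce.

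**1. Sign.** Fit ln C = a + b·t over the terminal points. Then lambda-z = −b and half-life = ln 2 / lambda-z. For exact exponential decay at 2, 3 and 4 h:

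| Profile | Slope b | lambda-z | Words (reject if slope > 0) | Symbol (reject if lambda-z > 0) |
|---|---|---|---|---|
| Half-life 1 h | −0.693 | +0.693 | keep | reject |
| Half-life 2 h | −0.347 | +0.347 | keep | reject |
| Half-life 4 h | −0.173 | +0.173 | keep | reject |
| Half-life 8 h | −0.087 | +0.087 | keep | reject |
| Rising: 1, 1.2, 1.5 | +0.203 | −0.203 | reject | keep |

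Words and symbol disagree on every row.

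**2. Tmax rule on the sampling grid.** The points are 0, 1, 2, 3 and 4 h.

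- Last measurable point 4 h: the last three are 2, 3 and 4 h, so tmax must be at 0 or 1 h.
- Last measurable point 3 h (SAP 6.10.5 sets later non-quantifiable values to missing): the last three are 1, 2 and 3 h, so no post-dose tmax qualifies.

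A profile whose observed peak is at the 2 h sample is excluded in both cases. The 10-minute window moves the nominal 1 h sample only to about 0.83–1.17 h. The Day 15 trough adds no point to the Day 1 profile. This step uses only figures in the documents.

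**3. Extrapolated share for a profile that qualifies.** The half-life is an assumption, because the documents give none. The model is one-compartment oral: C(t) = ka/(ka − ke) × (exp(−ke·t) − exp(−ka·t)), with ke = ln 2 / half-life and ka chosen so that ln(ka/ke)/(ka − ke) = 1 h. AUC0-4 is by the linear trapezoidal rule (the SAP's method), lambda-z comes from the 2, 3 and 4 h points, and share = (C4/lambda-z) / (AUC0-4 + C4/lambda-z).

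Worked case, half-life 4 h:

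- ke = 0.1733 and ka = 3.037 per hour.
- Concentrations at 0 to 4 h are 0, 0.841, 0.748, 0.631 and 0.530.
- AUC0-4 = 0.841 + 0.748 + 0.631 + 0.530/2 = 2.484 to rounding.
- lambda-z = (ln 0.7475 − ln 0.5303)/2 = 0.1717.
- Tail = 0.5303/0.1717 = 3.089.
- Share = 3.089/(2.484 + 3.089) = 55%.

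| Assumed half-life (h) | 1 | 1.3 | 2 | 4 | 8 | 12 |
|---|---|---|---|---|---|---|
| Extrapolated share of AUC0-inf | 15% | 20% | 32% | 55% | 74% | 82% |

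The share passes the SAP's 20% flag at a half-life of about 1.3 h, and is more than half at 4 h and above.

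**4. How many profiles might qualify.** This also rests on assumptions: 4,000 simulated profiles per scenario from the same model, half-life 3, 6 or 12 h, between-subject CV of Tmax 30% or 50%, 10% assay noise, and the sign rule applied as its words read.

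| Median true Tmax | Observed tmax at 1 h or earlier | Also R-squared at least 0.8 and a falling slope |
|---|---|---|
| 1.5 h | 29–43% | 8–34% |
| 2.0 h | 14–24% | 4–18% |
| 2.5 h | 6–14% | 2–10% |

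Essentially all qualifying profiles had more than 20% extrapolated. With the symbol coded literally, none qualified. At the protocol's Tmax of about 2 h and 9 to 17 subjects, the expected number is 0.04 × 9 = 0.4 to 0.18 × 17 = 3.1 per dose level if every subject reaches it.

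**The case against.** On the sign, a reader might infer that the SAP rejects every valid elimination constant and that no half-life will be produced. The documents do not support that as a certainty. It follows only if the symbol governs. The words in the same bullet state the usual exclusion, and the symbol is most naturally a slip in which the fitted slope was labelled lambda-z. Standard non-compartmental methods in Phoenix WinNonlin (SAP 6.10.2 and 8.1) make the literal reading unlikely to be followed. What stands is that an operative rule contradicts itself and has to be corrected.

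On Tmax, the rule is a sound safeguard against fitting half-life through the peak. Table 2 makes these parameters conditional, and 6.10.3 says that they will not be presented without a terminal elimination phase. Missing values are therefore expected. This stands as a reason to keep the rule. It does not answer the selection problem, because nothing tells the reader of a summary that the contributing profiles are early peakers.

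A reader might also infer that a typical subject can never qualify. That is too strong. Observed tmax varies between profiles and is read off an hourly grid, so a subject who usually peaks near 2 h may peak at the 1 h sample at some dose level. Nor is every qualifying AUC0-inf bound to exceed the 20% flag, since a half-life below about 1.3 h would not.

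The consequences are limited. The protocol's PK endpoints are AUC0-4, Cmax and Tmax (synopsis), with trough levels added in Protocol 9.8. None depends on lambda-z. Protocol 6.9 says that PK results do not drive escalation. That the figures might feed later dose planning is conjecture, which the documents do not support.

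**Conclusion.** The point holds in two parts, and its severity is minor.

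The sign contradiction in SAP 6.10.3 is established from the text alone and is wrong as written. It is a contradiction to correct, not a demonstrated loss of all estimates.

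The restriction to profiles with observed tmax at the nominal 1 h sample or earlier also follows from the documents alone, against an expected Tmax of about 2 h. The 6.10.4 summaries of lambda-z, half-life and AUC0-inf would therefore describe a selected subset, possibly a different one at each dose level.

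The sizes are illustrative. The extrapolated shares of 15% to 82% rest on a one-compartment model with Tmax 1 h and assumed half-lives of 1 to 12 h. The 4–18% of usable profiles rests further on an assumed spread of Tmax and assay noise. The primary efficacy analysis, the safety analyses and the protocol PK endpoints are untouched.

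**What to change.** In SAP 6.10.3, restate the condition so that lambda-z is not assigned if the slope of log concentration on time is zero or positive (lambda-z <= 0). Keep the Tmax safeguard unchanged.

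In SAP 6.10.4, do one of two things for lambda-z, half-life and AUC0-inf:

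- present them in listings only; or
- summarise them with the number of contributing profiles at each dose level, identify the values flagged for extrapolation, and state that they come from a subset selected for early peaks.

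Keep the summaries of Cmax, Tmax, AUC0-4 and AUC0-last.

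The cost is a short SAP wording change and, under the first option, the loss of summary tables for conditional parameters that are not protocol endpoints and that 4-hour sampling supports poorly. No change to sampling or data collection is needed.

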**Figure 3. Illustration of Imputation of Concentration at 4 Hours for Calculation of  $AUC_{0-4}$**

#### 6.10.4 Pharmacokinetic Summary and Analysis

Day 1 PK concentration data, within the acceptable sampling window, will be summarized for each time point using descriptive statistics from the PK Population (i.e., Mean, SD, Min, Max, Median, %CV, Geometric Mean, Geometric %CV) for each dose level. Plots of mean Day 1 concentrations of plasma ATR-101 and its metabolites (with standard deviation bars) versus nominal time will be generated for each dose level. Individual ATR-101 and metabolite concentration versus actual time plots will also be provided.

The Day 1 PK parameters will be summarized by dose level using the PK Population. Actual sampling times will be used. Geometric mean and geometric coefficient of variation (CV%) will be added to the descriptive statistics for  $C_{max}$  and all AUCs.

PK/PD relationships may be explored graphically.

#### 6.10.5 Handling Missing or Non-Quantifiable Data

Concentrations below the lower limit of quantitation (BLLOQ) before the first measurable concentration will be assigned a value of zero. A single BLLOQ value between measurable concentrations in a profile will be set to missing in the derivation of PK parameters, statistical analyses, and the individual subject plots. BLLOQ values that occur after the last measurable concentration will also be set to missing in the derivation of PK parameters and in the individual subject plots.

## **6.11 Safety Analyses**

Safety data includes AEs, physical examinations, vital signs, ECGs, and clinical laboratory assessments. Safety data will be summarized and listed. No formal statistical analysis of the safety data will be conducted. All safety summaries will be based on the Safety Population. Safety summaries will be based on observed values only.

### **6.11.1 Adverse Events**

AEs will be coded and classified by system organ class and preferred term using the Medical Dictionary for Regulatory Activities (MedDRA). All AEs reported for enrolled subjects during the clinical study will be recorded on the electronic case report form (eCRF). All AEs, regardless of relationship to study drug or procedure, should be collected beginning from the time the subject signs the study consent. AEs in clinical investigation subjects include any change in the subject's condition. This includes symptoms, physical findings, or clinical syndromes.

TEAEs are defined as adverse events that happen for the first time on or after the first dose date (Dose Level 1 Day 1) of ATR-101.

An overview with counts of events and subjects will be provided by dose level and treatment at AE onset and overall for the incidence of AEs in the following categories:

- Any TEAE
- Maximum severity of TEAE
- Any study drug related TEAE
- Maximum severity of study drug related TEAE
- Any serious treatment-emergent SAE (TESAE)
- Any study drug related SAE
- Death due to AE
- AE leading to discontinuation from study
- Study drug related AE leading to discontinuation from study

The incidence of TEAEs will be summarized by dose level and treatment at AE onset and overall by system organ class and preferred term. System organ class will be sorted alphabetically and preferred term will be sorted by descending total frequency within system organ class. Similar summaries will be provided for TEAEs by maximum severity. The same summaries will be done for study drug related TEAEs.

The AE summaries will be provided by dose level and treatment at AE onset. In other words, AEs starting on or after ATR-101 and prior to the subsequent Placebo dose will be attributed

to ATR-101. AEs starting on or after Placebo and prior to the subsequent ATR-101 dose will be attributed to Placebo.

Listings will be provided for any SAEs, AEs leading to discontinuation from study, and AEs beginning in the Placebo Baseline Lead-In Period.

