6.12.2 Assessing Severity of Adverse Events

The assessment of severity must be based on the Investigator's clinical judgement. Maximum severity should be assigned to one of the following categories:

- **Mild:** An AE which is easily tolerated by the subject, causing minimal discomfort and not interfering with everyday activities.
- **Moderate:** An AE which is sufficiently discomforting to interfere with normal everyday activities.
- **Severe:** An AE which prevents normal everyday activities.

An AE which is assessed as severe should not be confused with a serious AE. Refer to Section 6.12.5 for the definition of a serious AE.

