**Figure 2. Dosing Regimen per Dose Level**

ATR-101 BID	Day 1	Day 2	Day 3	Day 4	Day 5	Day 6	Day 7
	Day 8	Day 9	Day 10	Day 11	Day 12	Day 13	Day 14
Placebo BID	Day 15	Day 16	Day 17	Day 18	Day 19	Day 20	Day 21
	Day 22	Day 23	Day 24	Day 25	Day 26	Day 27	Day 28

Subjects will return to the study center after completion of the 14-day placebo Washout Period and will follow one of two actions based upon **Day 15** efficacy results:

- If the primary outcome measure is met (i.e., **17-OHP** ≤ **2xULN**) the subject completes the Final Study Visit
- If the primary outcome measure is **not** met (i.e., **17-OHP** > **2xULN**) the subject continues to the next dose level.

Table 1 below presents the 5 ATR-101 Dose Levels. Dose Levels 2, 3, 4, and 5 will follow the same procedures as Dose Level 1 (i.e., treatment with ATR-101 for 14 days, followed by the placebo Washout Period of 14 days). A subject may receive a minimum of one dose level (Level 1) or a maximum of 5 dose levels (Level 1-5), along with the corresponding placebo Washout Periods.

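### AE tables place each event's maximum severity under the dose level of onset, so an event that worsens at a later, higher dose can be counted under a lower dose or placebo

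*SAP*

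**What the plan says.** SAP 6.11.1 fixes the layout of the AE tables. For the overview: "An overview with counts of events and subjects will be provided by dose level and treatment at AE onset and overall". Its rows cover treatment-emergent events (TEAEs), maximum severity, relatedness to study drug, serious events, deaths and "AE leading to discontinuation from study". The tables by system organ class and preferred term use the same columns, and "Similar summaries will be provided for TEAEs by maximum severity". The section then restates the rule generally: "The AE summaries will be provided by dose level and treatment at AE onset". Only the start date decides placement: "AEs starting on or after ATR-101 and prior to the subsequent Placebo dose will be attributed" to ATR-101, with the mirror-image rule for events starting in washout. The definition reads: "TEAEs are defined as adverse events that happen for the first time on or after the first dose date (Dose Level 1 Day 1) of" the active drug. It has no clause for worsening.

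Protocol 6.12.2 governs grading as mild, moderate or severe: "Maximum severity should be assigned to one of the following categories". Neither document says whether an increase in severity is dated or starts a new record.

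The same subjects move through the columns. SAP 5.1 and its Table 1 take a subject through one to five levels, from 125 mg BID to 1000 mg BID. Each level is 14 days of ATR-101 followed by 14 days of placebo.

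**The concern.** In a within-subject escalation, the by-dose AE tables are a main description of how tolerability changes with dose. Safety is part of the primary objective, and SAP 6.11 plans no formal safety analysis, so readers will rely on these tables.

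Pairing the peak grade with the onset dose combines two facts that may belong to different doses. An AE that is mild at one level and severe two levels later would show as severe at the lower level, and its severe phase would not show at the higher one. If it began in washout, it would show as severe under placebo. The error has a direction: doses only rise, so worsening is always moved to an earlier period. The overall column is unaffected.

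**Working it through.** The plan states no figure that depends on this rule, so there is nothing to reproduce. The check applies the written rules to a hypothetical event.

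**1. Calendar.** With 28-day levels (SAP 5.2), level *k* has active days 28(*k* − 1) + 1 to 28(*k* − 1) + 14, counted from Level 1 Day 1.

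| Level | Dose | Active days | Washout days |
|---|---|---|---|
| 1 | 125 mg BID | 1–14 | 15–28 |
| 2 | 250 mg BID | 29–42 | 43–56 |
| 3 | 500 mg BID | 57–70 | 71–84 |
| 4 | 750 mg BID | 85–98 | 99–112 |
| 5 | 1000 mg BID | 113–126 | 127–140 |

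**2. Persistence needed** for an event that starts on the last active day of Level 1 (Day 14):

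- to Level 2 dosing: 29 − 14 = 15 days, across one washout
- to Level 4 dosing: 85 − 14 = 71 days, across three washouts
- to Level 5 dosing: 113 − 14 = 99 days, across four washouts

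An event starting on washout Day 28 and worsening on Day 29, under the next ATR-101 dose, needs one day. It would be booked to placebo.

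**3. Where the event lands.** Assume one record per AE: mild onset in Level 1 active dosing, severe at a later level.

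| Column | By onset (SAP 6.11.1) | By highest severity in each period |
|---|---|---|
| Level 1, ATR-101 | 1 severe | 1 mild |
| Later level, ATR-101 | 0 | 1 severe |

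If the peak is moderate, the same shift occurs in the moderate row.

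**4. Weight of one event.** SAP 6.3.2 uses subjects dosed at the level as the denominator. At Level 1 that is taken as 9 to 17 (SAP 5.1):

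- 1/9 = 11.1%
- 1/17 = 5.9%

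The number reaching the higher levels is not given. For assumed numbers of 3, 5, 9 and 17, one event missing from that column is 33.3%, 20.0%, 11.1% and 5.9%.

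**5. Discontinuation row.** The overview puts an AE that leads to withdrawal at its onset level. SAP 6.4 presents early withdrawals, with reason, by ATR-101 dose level. Read naturally, that is the level at which the subject withdrew. The two tables could then put the same withdrawal in different columns.

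**The case against.** The case for leaving the plan alone has several good points.

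- **One record per AE is an assumption.** The eCRF is not available. Protocol 6.12.1 counts any change in the subject's condition as an AE, and Protocol 6.12.4 speaks of occurrence or worsening when judging causality. Both are compatible with a new record on worsening, which would have its own onset at the higher dose. This stands as a limit on the finding. Assigning a maximum severity nevertheless suggests a single record. A new record might also fail the SAP's first-time test for a TEAE.
- **Long persistence is unlikely.** A Level 1 to Level 4 case must survive three placebo washouts, and each escalation requires that there be no safety issues. That stands. It does not cover adjacent levels, where 15 days or fewer suffice, and the documents do not say that a mild ongoing AE blocks escalation.
- **Other outputs help.** SAP 6.11 lists safety data. SAP 6.11.1 lists SAEs and AEs leading to discontinuation. Protocol 9.7 plans to tabulate treatment discontinuations. With 9 to 17 subjects, individual cases can be looked up. This stands for SAEs and withdrawals. For other events, a listing shows the dose at worsening only if that date was collected. The summaries by last dose level in SAP 6.2 do not say that an onset-assigned AE moves to a later dose.

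A reader might also infer three stronger points, which the documents do not support:

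- **That high doses will look free of toxicity.** New events at Levels 4 and 5 are booked there, and laboratory values, vital signs and ECGs are summarized within each level whatever the AE onset date (SAP 6.11.2 to 6.11.4).
- **That an AE forcing withdrawal is thereby shown as severe.** Discontinuation is a separate row from severity.
- **That the dose at which subjects stopped is lost.** The disposition table and the listings cover it.

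**Conclusion.** The point holds in a limited form. SAP 6.11.1 has an explicit rule, and with one maximum grade per AE it counts worsening at a later dose under the earlier dose, or under placebo for washout onset. One such event changes the Level 1 severity row by 5.9 to 11.1 percentage points (17 to 9 subjects) and can matter more at a sparsely populated higher level.

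This rests on two assumptions: worsening does not open a new record, which Protocol 6.12.2 suggests and no document settles; and at least one event persists into the next level and worsens there. The documents give no rate for such events. Adjacent-level cases are the realistic ones. The discontinuation row is a smaller matter of agreement with the disposition table. The change is worth making because it is cheap and leaves the existing incidence table intact.

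**What to change.** 1. **eCRF completion instructions:** require the date of any increase in AE severity, or a new record at that date. If a new record is chosen, state in SAP 6.11.1 that it counts as treatment-emergent.
2. **SAP 6.11.1, severity:** add a maximum-severity table that counts each subject in each dose level and treatment period by the highest severity present in that period.
3. **SAP 6.11.1, discontinuation:** show AEs leading to discontinuation by the dose level being taken at discontinuation, so that the row agrees with the disposition table in SAP 6.4.
4. **Keep** the onset-based incidence tables as they are.

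The cost is one eCRF instruction and some extra programming. Item 3 appears to need only the dosing dates already used in SAP 6.7. For data already collected without a date of worsening, sites would have to be queried or the gap footnoted. The downside is that an ongoing AE can appear under more than one level, so columns will not add up to the number of events. A footnote should say so.
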